10.1 All Adverse Events

A summary of incidence rates of individual AEs by System Organ Class (SOC) and Preferred Term (PT) will be prepared. Because a subject may experience more than one AE, summaries will provide both the number of subjects experiencing at least one event and the number of events. Percentages provided will be the percent of subjects experiencing one or more adverse events.

A listing of all adverse events will be provided which includes subject number, AE number, days since procedure, AE SOC and PT, severity of AE, whether or not the AE is classified as serious (SAE), the relationship to investigational device, relationship to procedure, relationship to other etiology, the action taken, and the outcome.

10.2 Adverse Events Leading to Withdrawal

A summary of incidence rates of individual AEs leading to withdrawal by SOC and PT will be prepared. A data listing of AEs leading to withdrawal will also be provided, displaying details of the event(s) captured on the CRF.

10.3 SERIOUS ADVERSE EVENTS

A summary of incidence rates of individual SAEs by SOC and PT will be prepared. Because a subject may experience more than one SAE, summaries will provide both the number of subjects experiencing at least one event and the number of events. Percentages provided will be the percent of subjects experiencing one or more adverse events.

A listing of all serious adverse events will be provided which includes subject number, AE number, days since procedure, AE SOC and PT, severity of AE, whether or not the AE is classified as serious (SAE),

Rev A

CONFIDENTIAL

the relationship to investigational device, relationship to procedure, relationship to other etiology, the action taken, and the outcome.

10.4 TREATMENT OR PROCEDURE RELATED ADVERSE EVENTS

A summary of incidence rates of individual treatment or procedure related AEs by SOC and PT will be prepared. Because a subject may experience more than one AE, summaries will provide both the number of subjects experiencing at least one event and the number of events. Percentages provided will be the percent of subjects experiencing one or more adverse events.

A listing of all treatment or procedure related adverse events will be provided which includes subject number, AE number, days since procedure, AE SOC and PT, severity of AE, whether or not the AE is classified as serious (SAE), the relationship to investigational device, relationship to procedure, relationship to other etiology, the action taken, and the outcome.

10.5 Deaths

Should any subjects die during the course of the VAST trial, relevant information will be supplied in a data listing.

11 OTHER PLANNED ANALYSES

11.1 PRIMARY ANALYSIS ACCORDING TO TREATMENT RECEIVED

A sensitivity analysis will be performed for the primary endpoints according to treatment subjects received, regardless of their initial randomization.

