15.5	Site Initiation	49
15.6	Monitoring	50
15.7	Required Reports	50
16	STUDY REQUIREMENTS	52
16.1	Quality Assurance	52
16.2	Monitoring	53
17	PROCEDURES AND INSTRUCTIONS	55
17.1	Special safety-related procedures	55
17.2	Administrative procedures	55
17.3	Ethics and Good Clinical Practice	55
APPEND	DIX A - STUDY SCHEDULE	56
APPEND	DIX B- Supplemental TRANSPLANTATION /OTHER APPENDICES	58
APPEND	DIX C – Supplemental TRANSPLANTATION	59
REFEREI	NCE LIST	60

CONFIDENTIAL	Clinical Protocol	DATE	Р	age
		9Dec2019		T
	mented Disc Regeneration in the Treatment of the or without Intervertebral Disc Herniation –	WRITER TG, DB, PW	NO. 9	REV 6

STUDY CONTACTS

Sponsor: Vivex Biologics, Inc.

[name]

[contact]

Medical Monitor: H. [name]

Chief Medical Officer Vivex Biologics, Inc.

[contact]

Clinical Representative: [name]

Clinical Program Manager

Vivex Biologics, Inc.

[contact]

Principal Investigator: [name]

[name]

[name]

[name] [contact]

CONFIDENTIAL	Clinical Protocol	DATE 9Dec2019	P	age
	mented Disc Regeneration in the T reatment of the or without Intervertebral Disc Herniation –	WRITER TG, DB, PW	NO. 10	REV 6

PROTOCOL SYNOPSIS

Title	Viable Allograft Supplemented Disc Regeneration in the Treatment of Patients with Low Back Pain with or without Intervertebral Disc Herniation – VAST Trial
Objective	To evaluate the safety and efficacy of viable allograft transplantation for the treatment of patients with symptomatic disc degeneration and tissue loss
Study Design	Multi-center, prospective, parallel, triple arm study to assess patients who participated in the VAST trial and receiving either viable allograft, saline, or allograft after cross-over. These patients will be evaluated at baseline, injection, 6 months, and 12 months. Subjects will then have an option for a 24 months and 36 months extension after their index procedures. Patients who received saline or active allograft in the VAST study, will be allowed to receive viable allograft and followed for an additional 12 and 24 months after that election. These subjects will need to meet initial inclusion/exclusion criteria again before another injection.

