6.9 Study Duration

The study duration for all enrolled subjects in this trial is approximately 12.5 months, including a 2-week Screening Phase for enrollment following initiation of consent documentation, 12 months of follow-up after treatment in the Active Phase, and an optional long term follow up period of an additional 24 months. Study enrollment is anticipated to require approximately 3-6 months. Therefore, the total study duration will be approximately 39.5 – 42.5 months. Subjects who have unremitting pain, or worsening conditions and who had been randomized to

CONFIDENTIAL	Clinical Protocol	DATE	P	age
		9Dec2019		1
TITLE: V iable A llograft S upplemented Disc Regeneration in the T reatment of		WRITER	NO.	REV
Patients with Low Back Pain wit	th or without Intervertebral Disc Herniation –	TG, DB, PW	28	6
VAST-001-017				

the conservative group will be evaluated clinically and be given the option to crossover into the allograft supplement group. All randomized subjects will have the option to receive the allograft treatment during the optional long term follow up at 24 months. These subjects will fill out questionnaires at 36 months and have the opportunity to do so over the phone.

This study may be terminated by the sponsor if deemed necessary and documented by an amendment to this protocol. If the study is terminated, the sponsor will support follow-up of those subjects who entered the study as though the study had not been terminated.

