7.1.4 Conservative Treatment Group 3 Months (± 14 days), or VA3

Patients randomized to the conservative arm will be evaluated with VASPI, ODI, SF-36 questionnaires as well as complete all required additional assessments as outlined in Appendix A during the 3 months visit. Patients will be evaluated for deteriorating or improving conditions relative to enrollment. Subjects who have experienced a significant decline in condition defined as a 10% increase in pain by VASPI, or a 9-point increase in ODI will be offered the allograft treatment as a crossover. If the subject does not meet the aforementioned changes in ODI or VASPI, or is considering withdrawal, they may also be offered the allograft treatment by physician discretion if condition has significantly declined. Subjects that crossover do not have to re-consent. The crossover allograft treatment can occur at any time period after the 3-month follow-up visit. To administer the crossover allograft treatment, a new visit will be scheduled and this visit will be considered as the new Active Phase Day 0. In addition to the 3 months follow-up visit assessments, these crossover subjects will receive a MRI and X-ray prior to the allograft treatment. All assessments done at this 3 months follow-up visit will be considered as the new baseline assessments. These crossover subjects will receive follow-up visits at 6 months and 12 months after allograft treatment. Crossover subjects will not be replaced by enrolling new patients in the conservative care treatment group.

7.1.5 Active Phase Month 6 (± 30 days) or VA4:

All randomized subjects will return to the clinic 6 months (± 30 days) subsequent to treatment for all safety and efficacy assessments as outlined in Appendix A. ODI, VASPI, and SF-36 questionnaires will be completed by the subject, and assisted by physician or physician designee. All subjects (excluding conservative care crossover subjects) will be randomized to include MRI at 6-month (MRI or no MRI, ratio 1:1) follow-up in addition to all other assessments. This randomization is performed to assess whether predictability at 6 months indicates performance at 12 months. The conservative care subjects that crossover to the allograft treatment group will all receive an MRI at 6-month follow-up after allograft treatment. All subjects will receive an X-ray at the 6-month follow-up visit. Additionally, a review of resource utilization since the Day 0 visit will be completed.

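### SAP 11.1 regroups conservative-care crossovers by treatment received, which selects on the outcome, so it cannot check the effect of crossover on allograft versus conservative care

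*SAP*

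**What the plan says.** SAP 11.1 repeats the analysis of both co-primary endpoints "according to treatment subjects received, regardless of their initial randomization". It does not mention crossover, and it gives no baseline or time origin for patients who change treatment.

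Protocol 7.1.4 sets the Month 3 trigger for offering allograft to conservative-care patients: "a 10% increase in pain by VASPI, or a 9-point increase in ODI". Patients below the trigger are covered too: "they may also be offered the allograft treatment by physician discretion if condition has significantly declined". Section 8.4 repeats both rules. Section 7.1.4 lets the injection take place at any time after the Month 3 visit and does not replace crossovers. Section 6.9 is worded more widely: "Subjects who have unremitting pain, or worsening conditions and who had been randomized to" conservative care may be given the option. That wording and 7.1.4 need to be reconciled.

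For crossovers, 7.1.4 also states: "All assessments done at this 3 months follow-up visit will be considered as the new baseline assessments". On timing it says: "These crossover subjects will receive follow-up visits at 6 months and 12 months after allograft treatment".

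The primary efficacy analysis (SAP 6.2 and 9.1) uses the mITT population as randomised, with a three-group Kruskal-Wallis test of the pre-post difference. The other checks on the primary endpoints are LOCF for missing data (SAP 7.3) and the per-protocol set, which drops major violations (SAP 6.3, 7.4). Neither deals with crossover that the protocol permits.

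**The concern.** A conservative-care patient receives allograft because an earlier value of the endpoint was bad. An analysis by treatment received takes such patients out of conservative care and puts them with allograft. The two groups then differ in prognosis even if allograft does nothing.

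SAP 11.1 is the only planned analysis in which crossovers change group, so readers will take it as the check on crossover. For allograft versus conservative care, disagreement with the primary result could be pure selection, and agreement would not be reassuring because a real benefit is shrunk.

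**Working it through.** **What the plan gives.** Neither document states a crossover rate, a correlation between visits or an expected bias, so there is no planned figure for this point to reproduce. The inputs in Protocol 13.3 and SAP 4 are an SD of 15.5, a worst-case reliability of 0.75 and a relevant difference of 9 points. From these, 15.5 × √(1 − 0.75) = 7.75 and Φ(−9/(15.5 × √2)) = 0.341, both as stated. The stated 40 per group does not reproduce: Noether's formula gives (1.960 + 0.842)² / (6 × 0.159²) ≈ 52. That is a separate matter and is not used below.

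**Model A (no treatment effect).** Worsening in ODI at Months 3 and 12 has mean 0, SD 15.5 and correlation ρ. Assumptions: 15.5 is the SD of change (the documents do not say), only the 9-point ODI trigger operates, and everyone offered allograft accepts. For ρ = 0.5:

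1. Fraction crossing over: 1 − Φ(9/15.5) = 0.281, or 11.2 of 40.
2. Their mean Month 3 worsening: 15.5 × φ(0.581)/0.281 = 18.6 points.
3. Their mean Month 12 worsening: 0.5 × 18.6 = 9.3 points.
4. Mean improvement of those left in conservative care: 0.281 × 9.3/0.719 = 3.63 points.
5. Mean improvement of the enlarged allograft group, original baseline: −(11.2 × 9.3)/151.2 = −0.69. With the reset baseline the crossovers appear to improve by 18.6 − 9.3 = 9.3 through regression to the mean, giving +0.69.
6. Allograft minus conservative care: −0.69 − 3.63 = −4.32 (original) and 0.69 − 3.63 = −2.94 (reset).

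With the original baseline, 3.63 of the 4.32 points comes from who remains in conservative care. Repeating this over ρ (negative is against allograft), with simulated Kruskal-Wallis rejection at 0.05:

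| ρ | vs conservative care, original / reset | vs placebo, original / reset | Rejection, original / reset |
|---|---|---|---|
| 0.1 | −0.9 / +0.5 | −0.1 / +1.2 | not run |
| 0.25 | −2.2 / −0.8 | −0.4 / +1.0 | not run |
| 0.3 | −2.6 / −1.2 | −0.4 / +1.0 | 9% / 6% |
| 0.5 | −4.3 / −2.9 | −0.7 / +0.7 | 21% / 13% |
| 0.7 | −6.1 / −4.7 | −1.0 / +0.4 | 38% / 26% |

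As randomised with the original baseline, rejection is about 5%. For ρ from 0.25 to 0.7, 50% uptake reduces the bias against conservative care to −0.9 to −2.6 (original) or −0.2 to −1.9 (reset). A 10-point average improvement in everyone, with full uptake, gives −1.0 to −2.9 or −0.5 to −2.4.

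**Model B.** This uses the plan's measurement error of 7.75 at each visit, with an assumed SD of true change of 0 to 10 points per period. Then 20.6% to 27.2% cross over. The bias against allograft versus conservative care is 2.4 to 5.9 points (original) or 1.5 to 4.6 (reset). At 50% uptake with the original baseline it is 1.0 to 2.6. A true 9-point benefit would appear as 9 − 2.4 = 6.6 down to 9 − 5.9 = 3.1.

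**Check of the remedy.** Under Model B, regression imputation of crossovers from baseline and Month 3 gave mean differences of −0.02 to 0.08 when the truth is 0, and 8.97 to 9.08 when the truth is 9. With one assumed later, unrecorded trigger between Months 3 and 6, a bias of 0.9 to 2.2 points remained with no effect.

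**The case against.** The strongest reply is that nothing is decided by 11.1. Success rests on the as-randomised tests in SAP 9.1, and a treatment-received analysis beside an as-randomised primary is common. That stands, and it limits the point to how a secondary result can be read. It does not rescue 11.1 as a check: a sensitivity analysis that departs from the null through selection alone neither supports nor challenges the primary result for this comparison.

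The size is also open to challenge, rightly. Uptake is optional and average improvement is plausible; both shrink the bias. At ρ = 0.1 with the reset baseline the sign reverses.

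Four stronger readings are tempting but not supported:

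- That 11.1 penalises allograft in general. Against placebo the shift is about 1 point or less, and under the reset baseline it mostly favours allograft.
- That only patients who did not worsen remain in conservative care. Decliners may refuse the offer, and the wording of 6.9 lets patients with unremitting pain leave.
- That the synopsis already makes crossovers a separate group. Its phrase "receiving either viable allograft, saline, or allograft after cross-over" omits conservative care and leads into the extension, so it may not refer to Month 3 crossovers.
- That imputing on recorded scores removes the selection. Crossover may be discretionary and may come at any time after Month 3.

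**Conclusion.** The point holds in a limited form. That 11.1 selects on the outcome follows from the text alone. The direction, usually against allograft relative to conservative care when there is no effect, and the size are model results. They are roughly 2 to 6 ODI points with the original baseline, full uptake, no average improvement and ρ of about 0.25 to 0.7; about 1 to 5 with the reset baseline; and mostly below 3 at 50% uptake. Three-group Kruskal-Wallis rejection with no effect runs from about 6% to 38% across the scenarios simulated.

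Correlations, uptake, average change and the reading of 15.5 as an SD of change are assumptions. The models treat the crossovers' final score as a Month 12 score, although their last visit falls later. The VASPI endpoint was not quantified, because the documents give no SD for it.

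A reader might infer that the trial's main conclusion is compromised. The documents do not support that, because 11.1 leaves the as-randomised analysis unchanged. What is lost is the only planned look at crossover for allograft versus conservative care. The SAP should be changed, but this is not critical.

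**What to change.** Make the crossover sensitivity analysis in SAP 11.1 the following:

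- Keep all three arms as randomised, with the original baseline and time counted from randomisation.
- Set conservative-care ODI and VASPI after the allograft injection to missing.
- Multiply impute them from all ODI and VASPI scores recorded before crossover: baseline, Month 3, and Month 6 where it precedes the injection.
- Report crossovers as a separate descriptive group, not pooled with randomised allograft, and flag discretionary and later crossovers.

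If the treatment-received analysis is kept, label it non-randomised and descriptive, and state its baseline and time origin. State the baseline for crossovers in SAP 9.1 as well. If the reset baseline were applied to crossovers kept in conservative care, simulated Kruskal-Wallis rejection with no effect was 35% to 41% under Model A, in favour of conservative care.

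The cost is SAP wording and one imputation program, with no new data or visits. The imputation assumes that crossover is explained by recorded scores. When uptake is high, few conservative-care patients above the trigger remain to inform it, so it extrapolates. For discretionary or later crossovers it reduces the bias but does not remove it. It should be presented as one stated strategy on those terms.

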11.2 Responder Analyses

A responder analysis will be performed for both primary endpoints. For the ODI, a subject with at least a 15-point reduction will be considered a responder. For the VAS, a subject with at least a 50% reduction will be considered a responder. The chi-square test of independence will be used to compare the percent of subjects considered a responder in each treatment group.

Additionally, regressions will be used to determine whether any characteristics are associated with responder status.

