7.5 MULTIPLE COMPARISONS AND MULTIPLICITY

For the trial to be considered a success, both co-primary outcomes, the ODI and the VAS, must be statistically significant at an overall two-sided α -level of 0.05. Additionally, for each primary outcome, if the Kruskal-Wallis test is significant, pairwise comparisons will be analyzed using the Dwass, Steel, Critchlow-Fligner method, which controls the overall family-wise error rate.

No adjustments for multiple testing will occur for secondary endpoints, as the intention of these analyses is exploratory in nature.

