9.2 SECONDARY ENDPOINTS

All secondary variables will be analyzed in an exploratory way, with no adjustment for multiple testing. The secondary endpoints include:

- Improvement in ODI and VASPI at 6 months
- Improvement in ODI, SF-36, and VASPI at 6 and 12 months after treatment
- MRI measurements at 6 and 12 months after treatment
- Adverse Event (AE)/ Serious Adverse Events (SAE) rates after treatment
- Hospitalization rate at 12 months after treatment
- Re-operation rate at 12 months after treatment
- Resource utilization following treatment at 6 and 12 months after treatment
- Changes in laboratory tests

Improvement in ODI, VASPI, and SF-36 will be analyzed similar to the primary endpoint, using the Kruskal-Wallis test to test for an overall difference between the three treatment groups. If the overall test is significant, the Dwass, Steel, Critchlow-Fligner Method will be used to asses all pairwise comparisons.

Adverse event rates, serious adverse events rates, hospitalization rates, and re-operation rate will be summarized by treatment group and compared using the chi-square test of independence or Fisher's exact test, as appropriate.

MRI data will be summarized by treatment group as mean at each timepoint, and mean change from baseline. Analyses will be done focusing on the level treated, but additional analyses will be completed which examine all five levels to see if there are adjacent level effects. Group comparisons will be made using the Krusal-Wallis test. If the overall test is significant, the Dwass, Steel, Critchlow-Fligner Method will be used to assess the pairwise comparisons.

Resource utilization and changes in laboratory tests will be summarized by treatment group.

10 Adverse Events

All adverse events will be coded using the standardized Medical Dictionary for Regulatory Activities (MedDRA) central coding dictionary, version 22.1 or greater.

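### Responder, AE, SAE, hospitalisation and re-operation rates get only a three-group test, with no allograft-saline contrast or confidence interval planned

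*SAP*

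**What the plan says.** SAP 11.2 defines two responder outcomes: "For the ODI, a subject with at least a 15-point reduction will be considered a responder", and "For the VAS, a subject with at least a 50% reduction will be considered a responder". The planned comparison is: "The chi-square test of independence will be used to compare the percent of subjects considered a responder in each treatment group". The section adds that "regressions will be used to determine whether any characteristics are associated with responder status", which names no treatment contrast.

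SAP 9.2 covers four further rates: "Adverse event rates, serious adverse events rates, hospitalization rates, and re-operation rate will be summarized by treatment group". These are to be "compared using the chi-square test of independence or Fisher's exact test, as appropriate". Nothing follows that sentence on pairs of arms.

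The rank-based outcomes are handled differently. SAP 7.5 states that "for each primary outcome, if the Kruskal-Wallis test is significant, pairwise comparisons will be analyzed using the Dwass, Steel, Critchlow-Fligner method", and SAP 9.1 repeats this for ODI and VASPI. For secondary ODI, VASPI and SF-36, SAP 9.2 says: "If the overall test is significant, the Dwass, Steel, Critchlow-Fligner Method will be used to asses all pairwise comparisons". The MRI paragraph of 9.2 contains the same step.

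SAP sections 4 and 9.1 define three groups: allograft (140), placebo (40) and conservative care (40). That the binary tests run across all three is inferred from this. Neither section restricts them to a pair.

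**The concern.** The two comparators answer different questions. Under Protocol 6.3, patients given allograft or saline are not told which they received, while conservative-care patients know their assignment. Allograft versus saline therefore isolates the product. A difference from conservative care also carries the injection procedure and the patients' expectations, and ODI and VASPI are self-reported.

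A two-degree-of-freedom test cannot separate these explanations. A statement that responder rates differed at p < 0.05 could rest wholly on the conservative arm. On the safety side, a significant AE comparison would not show whether the product or the injection lies behind it.

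SAP section 13 justifies the Dwass-Steel-Critchlow-Fligner step by the need to see which comparisons differ. The same need applies to these six binary comparisons, but that method works on ranks and is not assigned to them.

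**Working it through.** **Inputs from the documents.** Group sizes 140/40/40 (SAP section 4). Two-sided 0.05 is the level stated for the secondary outcomes (SAP section 2). SAP 11.2 states no level, so 0.05 is assumed for responders. No responder or event rate is given for any arm, and no power figure for any binary comparison. The plan's one sample-size figure, 40 per group, concerns a two-group Wilcoxon test on ODI and is not used here. All rates below are assumptions for illustration.

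**Step 1: one table.** Take 70/140 allograft, 20/40 saline and 10/40 conservative responders (50%, 50%, 25%).
- Pooled rate: 100/220 = 0.4545. Expected responders: 63.64, 18.18, 18.18.
- Chi-square = Σ(O − E)² / [E(1 − 0.4545)] = (0.636 + 0.182 + 3.682) / 0.5455 = 8.25 on 2 df, p = exp(−8.25/2) = 0.016.
- Allograft versus saline: 50% against 50%, chi-square 0.00, p = 1.00.
- Risk difference 0, SE = √(0.25/140 + 0.25/40) = 0.090, 95% CI ±1.96 × 0.090, about −18 to +18 percentage points.

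The planned output for this table would be p = 0.016. The interval, which shows what is and is not known about the product, is not planned.

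**Step 2: how often this would happen.** Binomial simulation at 140/40/40, 40,000 trials per row. Each trial gets the three-group Pearson chi-square and the allograft-saline chi-square, both at 0.05. The last column is the three-group proportion minus the proportion in which both are significant.

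| Assumed true rates (allograft/saline/conservative) | Three-group significant | Both significant | Three-group significant, allograft v saline not |
|---|---|---|---|
| 50/50/30% | 0.541 | 0.046 | 0.495 |
| 50/50/25% | 0.759 | 0.048 | 0.711 |
| 50/50/20% | 0.918 | 0.049 | 0.869 |

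At 50/50/25%, 0.711/0.759 = 94% of the significant three-group results come without a significant allograft-saline difference.

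**Step 3: the opposite case.** Take 70/140, 12/40 and 20/40 (50%, 30%, 50%). The three-group test gives chi-square 5.26, p = 0.072. Allograft versus saline gives chi-square 5.02, p = 0.025 (Fisher 0.031). The risk difference is 20 points, SE = √(0.25/140 + 0.21/40) = 0.084, 95% CI about 4 to 36 points. A pairwise step that runs only after a significant overall test would leave this difference unreported, so the interval should not depend on that test.

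**The case against.** **These analyses carry little weight by design.** SAP 7.5 and 9.2 call the secondary outcomes exploratory, and the responder analysis sits in section 11 among the additional analyses. Success rests on ODI and VASPI alone, both of which have a pairwise step. The responder outcomes are dichotomised forms of the same scores. All of this stands and limits the severity.

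**The output is not blind to the pattern.** SAP section 7 generates results by treatment group, and 9.2 summarises the four rates by group. In the Step 1 table a reader would see 50% beside 50% and could compute an interval from the counts. This also stands. What remains is that no allograft-saline estimate is pre-specified, and under SAP sections 2 and 5.2 a later one would have to be labelled post hoc.

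**The 25% rate is an assumption.** Protocol 7.1.4 lets conservative-care patients cross over to allograft after the 3-month visit, and SAP 6.2 keeps them in their randomised arm. If allograft and saline both give 50%, crossover could pull the conservative rate towards 50%. The table therefore shows a range, and the frequency falls as the rates converge.

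**Stronger readings that the documents do not support.**
- A reader might infer that the three-group test generally loses power against a direct allograft-saline test. It depends on the conservative arm. At assumed responder rates of 60/35/60% the three-group test has about 75% power against 81% for the direct test. At 60/35/35% it has 91% against 81%.
- A reader might want the same simulation for adverse events. SAP 6.4 analyses them by treatment received, and crossover makes those denominators unknown, so 140/40/40 would not apply.
- A reader might take the AE comparison to be the only between-arm safety test. SAE, hospitalisation and re-operation rates are also tested.

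**Conclusion.** The gap is real but minor. All six binary comparisons end at an overall test with no pairwise step and no named contrast, unlike the rank-based outcomes in the same SAP. A significant result can arise from the conservative arm alone. At 140/40/40 with allograft and saline both at 50%, the three-group test is significant while allograft versus saline is not in about 49%, 71% or 87% of trials, for conservative rates of 30%, 25% or 20%. These figures rest on assumed rates and on full data in the randomised group sizes. They apply to the responder outcomes only.

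A reader might go further and infer that the trial's conclusion is at risk. The documents do not support that: success is defined on the two co-primary endpoints, and these comparisons do not enter the rule.

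**What to change.** In SAP 11.2 and in the paragraph of 9.2 on the four rates:

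1. Name allograft versus saline as the contrast to interpret for each binary outcome.
2. Report its risk difference with a 95% CI whether or not the three-group test is significant.
3. After a significant three-group test, add pairwise 2×2 chi-square or Fisher tests, labelled exploratory. This identifies the arms that differ but does not recover power: at 60/35/60% the allograft-saline test after the overall test succeeds in 72% of trials, against 81% when run directly. Item 2 therefore matters more.
4. For the safety rates, state that groups are as treated and that crossover from conservative care changes the denominators.

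The cost is SAP wording and a few table rows, with no new data and no change to the co-primary analysis. The downside is additional unadjusted exploratory intervals, which should be labelled as such.
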